#### 5.4.3.5.2. DLQI

#### 5.4.3.5.2.1. Definition

The DLQI is a dermatology-specific quality of life instrument designed to assess the impact of the disease on a participant's quality of life. It is a 10-item questionnaire that, in addition to evaluating overall quality of life, can be used to assess 6 different aspects that may affect quality of life: symptoms and feelings, daily activities, leisure, work or school performance, personal relationships, and treatment. The DLQI is calculated by summing the score of each question resulting in a maximum of 30 and a minimum of 0. A higher score indicates more severe disease. A score of  $\leq 1$  indicates no effect at all of disease on participant's health related quality of life, and a reduction of 5 points or more in total DLQI score is considered clinically meaningful improvement.

For a partially answered questionnaire (eg, not all 10 answers in the DLQI questionnaire were available):

- If one question's answer is not available, this question will be scored 0. The total score will then be calculated.
- If two or more questions' answers are unavailable, the questionnaire is not scored. Hence, the total score and each of the 6 component scores will be set to missing.
- If one question from one of the 6 component scores is missing, the affected component score will be set to be missing.

## 5.4.3.5.2.2. Analysis related to DLQI

- The change from baseline in DLQI scores at Week 12 and Week 16 will be compared between each of the bermekimab groups and the placebo group respectively. In addition, the change from baseline in DLQI scores will also be summarized over time.
- The proportions of participants with DLQI score of 0 and 1 at Week 12 and Week 16 for the participants with baseline DLQI score >1 will be compared between each of the bermekimab groups and the placebo group respectively and will also be summarized by treatment groups over time.
- The proportion of participants with a reduction of 5 or more points in DLQI score for the participants with baseline DLQI score  $\geq 5$  at Week 12 and Week 16 will be compared between each of the bermekimab groups and the placebo group and will also be summarized by treatment groups over time.
- The change from baseline in DLQI component scores at Week 12 and Week 16 will be compared between each of the bermekimab groups and the placebo group.

## 5.4.3.5.3. Hidradenitis Suppurativa Symptoms Diary (HSSD)

## 5.4.3.5.3.1. Definition

The HSSD is a 7-item patient self-reported questionnaire that assesses 5 HS-related symptoms including pain, tenderness, hot skin feeling, odor, and itchiness. The participants are asked to rate the severity of each symptom on a 0 to 10 numerical rating scale, with 0 indicating no symptom

experience and 10 indicating the worst possible symptom experience. All 5 symptoms have a recall period of the past 7 days, except for 2 additional questions on pain which evaluate current pain and pain in the past 24 hours. Each individual symptom scale score, ranging from 0-10, will be summarized. A total symptom score, which will also range from 0-10, will be derived by averaging the 5 individual scale scores that utilize the past 7-day recall period.

# 5.4.3.5.3.2. Analysis Related to Hidradenitis Suppurativa Symptoms Diary (HSSD)

- The change from baseline in HS-related skin pain in the past 24 hours based on HSSD at Week 12 and Week 16 will be compared between each of the bermekimab groups and the placebo group respectively.
- The change from baseline in each HSSD symptom scale score (7 days recall) and the change from baseline in current pain at Week 12 and Week 16 will be compared between each of the bermekimab groups and the placebo group.
- The change from baseline in HSSD total symptom score at Week 12 and Week 16 will be compared between each of the bermekimab groups and the placebo group.
- Number of participants with a reduction of ½ SD or more from baseline in HSSD total symptom score at Week 12 and Week 16 will be compared between each of the bermekimab groups and the placebo group.
- The change from baseline in each HSSD symptom scale score (7 days recall), the change from baseline for the past 24 hours pain and current pain, and the change from baseline in HSSD total symptom score will be summarized over time.

In addition, two supplementary analyses will be performed for the analyses (a) change from baseline in HS-related skin pain in the past 24 hours based on HSSD at Week 12 and week 16 and (b) change from baseline in HS-related skin pain in the past 24 hours based on HSSD overtime (Section 5.2.2) by using

- Observed data regardless of whether the subject discontinued treatment or have missing data.
- Data after treatment discontinuation will be considered as missing, missing data will be addressed by MMRM model.

# 5.4.3.5.4. Hospital Anxiety and Depression (HADS)

# 5.4.3.5.4.1. Definition

The HADS is an instrument for screening anxiety and depression in non-psychiatric populations; repeated administration also provides information about changes to a patient's emotional state. The HADS consists of 14 items, 7 each for anxiety and depression symptoms; Each item on the questionnaire is scored from 0-3 resulting in a score between 0 and 21 for either anxiety or depression. The following cut-off scores are recommended for both subscales: 7 to 8 for possible presence, 10 to 11 for probable presence, and 14 to 15 for severe anxiety or depression. The HADS is provided in the study reference manual.

If one or more of the items within each domain are left unanswered, that HADS component score will be considered missing.

## 5.4.3.5.4.2. Analysis Related to Hospital Anxiety and Depression

- The change from baseline in Hospital Anxiety and Depression scale (HADs) at Week 12 and Week 16 will be compared between each of the bermekimab groups and the placebo group.
- The change from baseline in Hospital Anxiety and Depression scale will be summarized over time by treatment groups.
- The proportion of participants with hospital anxiety scale <8 and depression scale <8 at Week 12 and Week 16 will be compared between each of the bermekimab groups and placebo groups, among participants with a baseline hospital anxiety scale and depression scale >=8.
- Hospital anxiety scale and depression scale shift from baseline with respect to the hospital anxiety and depression scale category (<8, >=8) will be summarized over time.

## 5.4.3.5.5. EuroQol Health Status Questionnaire (EQ-5D-3L)

## 5.4.3.5.5.1. Definition

The EQ-5D-3L consists of 2 pages: the EQ-5D descriptive system and the EQ visual analogue scale (EQ VAS).The EQ-5D-3L descriptive system comprises the following five dimensions: mobility, self-care, usual activities, pain/discomfort and anxiety/depression. Each dimension has 3 levels: no problems, some problems, and extreme problems. The patient is asked to indicate his/her health state by ticking the box next to the most appropriate statement in each of the five dimensions. This decision results into a 1-digit number that expresses the level selected for that dimension. The digits for the five dimensions can be combined into a 5-digit number that describes the patient's health state. The EQ VAS records the patient's self-rated health on a vertical visual analogue scale where the endpoints are labelled 'Best imaginable health state (scale of 100) ' and 'Worst imaginable health state (scale of 0)'. The VAS can be used as a quantitative measure of health outcome that reflects the patient's own judgement.

## 5.4.3.5.5.2. Analysis Related to Health Status Questionnaire (EQ-5D-3L)

- The change from baseline in EQ VAS scale at Week 12 and Week 16 will be compared between each of the bermekimab groups and the placebo group.
- The change from baseline in EQ VAS scale will be summarized over time by treatment group.
- Number of participants with a reduction of ½ SD or more from baseline in EQ VAS scale at Week 12 and Week 16 will be compared between each of the bermekimab groups and the placebo group.
- The distribution of health state scale for each of the EQ-5D-3L dimension at Week 12 and Week 16 will be compared between each of the bermekimab groups and the placebo group; and will also be summarized over time.

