## 5.3.4. Analysis Methods

The primary endpoint will be compared between the each bermekimab group and the placebo group. The primary endpoint will be analyzed at Week 12 based on the composite strategy (Section 5.3.2) and the data from all participants in FAS (Section 2.4.1.1) will be analyzed according to randomized treatment group regardless of the treatment actually received.

In this primary analysis, the number and proportion of participants who achieve a HiSCR at Week 16 will be summarized for each treatment group. To address the primary objective, a CMH chi-square statistic stratified by stratified by prior biologic use (yes/no) and screening Hurley stage (II/III) at an alpha level of 0.05 will be used.

The proportion of participants who achieve HiSCR at Week 12 will be compared between each of the 2 bermekimab treatment groups and the placebo group. The proportion difference between each bermekimab group and placebo group and its 2-sided 95% CI will be provided based on normal approximation with Mantel-Haenszel weights adjusting for prior biologic use (yes/no) and screening Hurley stage (II/III).

The study would be claimed as positive if any of the comparisons for primary endpoint analysis (weekly injection group vs placebo, and every other week injection group vs placebo) is less than or equal to 0.05. Therefore, an overall Type I error rate will be maintained at 0.1 or less for the primary endpoint analysis.

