## 5.4.3.5.7. Patient Global Impression of Severity (PGI-s)

## 5.4.3.5.7.1. Definition

The PGI-s is a single item patient reported outcome that assesses change in a patient's impression of their disease severity. The PGI-s item asks the respondent to best describe how his/her HS symptoms are now ("check the one number that best describes how your HS symptoms are now") on a 4-point scale scored as: "normal" (1), "mild" (2), "moderate" (3), or "severe" (4)".

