## 5.4.3.5.7.2. Analysis Related to PGI-s

- The distribution of the PGI-s scale at Week 12 and Week 16 will be compared between each of the bermekimab groups and the placebo group.
- The proportion of participants who achieved PGI-s of normal (0), normal (0) or mild (1) at Week 12 and Week 16 will be compared between each of the bermekimab groups and the placebo group respectively.
- Summary of PGI-s symptom status will be summarized over time.

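### Three SAP definitions are wrong as written: the EQ VAS count captures worsening, the PGI-s responder codes do not match the scale, and the primary analysis summarises HiSCR at Week 16 instead of Week 12

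*SAP*

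**What the plan says.** **EQ VAS.** SAP 5.4.3.5.5.1 labels the ends of the scale "Best imaginable health state (scale of 100") and "Worst imaginable health state (scale of 0"). SAP 5.4.3.5.5.2 then compares the arms at Weeks 12 and 16 on the "Number of participants with a reduction of ½ SD or more from baseline in EQ VAS scale". SAP 5.4.3.5.3.2 has a bullet of the same form for the symptom diary: "Number of participants with a reduction of ½ SD or more from baseline in HSSD total symptom score". On that diary a high score is bad, with "10 indicating the worst possible symptom experience" (5.4.3.5.3.1).

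**PGI-s.** SAP 5.4.3.5.7.1 describes the item "on a 4-point scale scored as: 'normal' (1), 'mild' (2"), continuing to moderate at 3 and severe at 4. Protocol 8.2 gives the same coding. The analysis in SAP 5.4.3.5.7.2 is "The proportion of participants who achieved PGI-s of normal (0), normal (0) or mild (1) at Week 12 and Week 16".

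**Primary analysis.** SAP 5.3.4 states: "In this primary analysis, the number and proportion of participants who achieve a HiSCR at Week 16 will be summarized for each treatment group". The same section says that the endpoint is analysed, and the arms compared, at Week 12. SAP 5.3.1 (definition), 5.3.2 (estimand) and 5.3.3 (data handling), and Protocol 10.5.3.1, all give Week 12. HiSCR at Week 16 is a secondary analysis (SAP 5.4.3.1.2).

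**The concern.** Each analysis rule disagrees with the definition it depends on, and someone programming from the text could produce a wrong output.

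- **EQ VAS:** a fall on a scale where high is good is a deterioration. An effective drug would show a lower rate than placebo in a list of endpoints that otherwise count benefit. The missing-data rule adds to this. SAP 5.2.2 makes discontinued and missing patients non-responders for binary secondary endpoints, so on this count dropouts would be scored as not having worsened, which is the favourable outcome.
- **PGI-s:** code 0 does not exist on the scale, and code 1 means normal, not mild.
- **Primary analysis:** the summary table could show one time point beside a test at another. Week 16 output is a realistic prospect, because the SAP plans a Week 16 database lock that includes HiSCR.

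SAP 1.5.2 has named sponsor staff unblinded at the Week 16 lock. A correction made after that would be open to challenge as a post hoc change of definition.

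**Working it through.** **The plan's own figure.** The sample size for Week 12 HiSCR (SAP 1.4) is not in dispute and reproduces. With rates of 0.60 and 0.30, mean rate 0.45 and two-sided alpha 0.05:

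n = [1.960 × √(2 × 0.45 × 0.55) + 0.842 × √(0.60 × 0.40 + 0.30 × 0.70)]² / 0.30² ≈ 42 per arm, with power 0.800.

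None of the three errors enters this calculation.

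**EQ VAS, first illustration.** The documents give no EQ VAS mean or SD, so the inputs are assumptions: normally distributed change, SD 20 for both the threshold and the spread of change, hence a threshold of 10 points. For mean change m:

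- as written: P(change ≤ −10) = Φ((−10 − m)/20)
- as improvement: P(change ≥ 10) = 1 − Φ((10 − m)/20)

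For m = +10 and +2, the as-written rates are Φ(−1.0) = 15.9% and Φ(−0.6) = 27.4%, a difference of −11.6 points. The improvement rates are 50.0% and 1 − Φ(0.4) = 34.5%, a difference of +15.5 points.

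| Mean change, drug / placebo | As written (difference) | Improvement (difference) |
|---|---|---|
| +10 / +2 | −11.6 | +15.5 |
| +8 / 0 | −12.4 | +15.2 |
| +12 / +4 | −10.6 | +15.8 |
| +15 / +5 | −12.1 | +19.7 |

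**EQ VAS, second illustration.** Here half an SD means half a baseline SD. With equal SDs at baseline and visit and correlation r, the SD of change is √(2(1 − r)) baseline SDs. At r = 0.5 this is 1. With a mean gain of 0.5 SD on drug and 0 on placebo:

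- as written: Φ(−1.0) = 15.9% against Φ(−0.5) = 30.9%
- improvement: 50.0% against 30.9%

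With r from 0.3 to 0.7, drug gain 0.5 to 0.8 SD and placebo gain 0 to 0.2 SD, the as-written rates run from 4.7% to 19.9% on drug and from 18.3% to 33.6% on placebo. The better arm has the lower rate in every case examined.

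**PGI-s.** Let p₁ and p₂ be the proportions scored normal (1) and mild (2).

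| Endpoint | Codes as written | Rate obtained | Rate intended |
|---|---|---|---|
| Normal | 0 | 0 in every arm | p₁ |
| Normal or mild | 0 or 1 | p₁ | p₁ + p₂ |

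The shortfall in the second row is p₂, all of the mild patients.

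**Primary analysis.** Within SAP 5.3.4, the sentences on the analysis time point and on the comparison of proportions say Week 12; the Mantel-Haenszel difference and its interval follow the latter. The summary sentence says Week 16. The sentence specifying the CMH test comes directly after the Week 16 sentence and names no week.

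**The case against.** The EQ VAS bullet uses neither the word responder nor improvement, so a deliberate count of worsening cannot be ruled out from that line alone. The rest of the SAP makes it unlikely. The threshold analyses for NRS, DLQI, HADS and PGI-s all count benefit. Where worsening is wanted, as with flares in 5.4.3.2.2, it is named and defined. The bullet also matches the HSSD wording, and non-responder imputation would make no sense for a deterioration count. It does stand that the mean change in EQ VAS is compared separately and is unaffected, so the reversal is limited to one derived count.

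On PGI-s, the verbal labels show what was meant, and only code 0 is actually off the scale. The wrong result follows only if the programmer uses the codes, and a 0% row in every arm would be noticed. The understated normal-or-mild row would be harder to spot.

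On HiSCR, one descriptive sentence is wrong and the rest of its section contradicts it. The endpoint, the estimand and the stated comparison remain at Week 12.

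The EQ VAS percentages rest on assumed inputs, leave out discontinuations, and depend on which SD is meant, which the SAP does not say. That limits what can be claimed about size, but not about direction.

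**Conclusion.** The concern holds for all three definitions. The EQ VAS rule points the wrong way. Under the first set of assumptions a drug advantage of 15.2 to 19.7 points would appear as a deficit of 10.6 to 12.4 points, and the second set, with varied correlation and gains, also reverses the direction throughout. Those sizes are illustrative; the direction follows from the scale anchors whenever the drug shifts EQ VAS upward relative to placebo with similar spread. The PGI-s codes, if applied literally, give 0% normal by construction and drop every mild patient from the broader category. The Week 16 sentence is an internal contradiction in the primary analysis section, not a change of primary endpoint.

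The EQ VAS and PGI-s analyses are secondary with nominal p-values, and nothing here alters sample size, power or type I error. The errors should be corrected because following the text produces wrong results, and the SAP's own definitions settle what the text should say.

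**What to change.** Make three corrections:

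1. **SAP 5.4.3.5.5.2:** replace the reduction with an increase (improvement) of half an SD or more in EQ VAS.
2. **SAP 5.4.3.5.7.2:** use normal (1), and normal (1) or mild (2).
3. **SAP 5.3.4:** change the summary of HiSCR from Week 16 to Week 12.

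Close two related gaps in the same edit. State which SD defines the half-SD threshold for both EQ VAS and HSSD, for example baseline SD or SD of change. Add Week 12 to the CMH sentence in 5.3.4.

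The cost is a few words, with no change to design, data collection or power. The edits should be made before programming and before anyone is unblinded at the Week 16 lock.

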## 5.4.3.5.6. Patient's Global Impression of Change (PGI-c)

#### 5.4.3.5.6.1. Definitions

The PGI-c is a single item patient reported outcome that assesses change in severity of skin pain due to HS. Participants will rate how his/her HS has changed since the beginning of the study using a 7-point scale ranging from 1 which indicates "very much better" to 7 which indicates "very much worse" with a neutral center point 4 which indicates ("no change").

## 5.4.3.5.6.2. Analysis Related to PGI-c

• The distribution of the PGI-c scale will be summarized over time by treatment group.

## 5.4.3.5.7. Patient Global Impression of Severity (PGI-s)

## 5.4.3.5.7.1. Definition

The PGI-s is a single item patient reported outcome that assesses change in a patient's impression of their disease severity. The PGI-s item asks the respondent to best describe how his/her HS symptoms are now ("check the one number that best describes how your HS symptoms are now") on a 4-point scale scored as: "normal" (1), "mild" (2), "moderate" (3), or "severe" (4)".

## 5.4.3.5.7.2. Analysis Related to PGI-s

- The distribution of the PGI-s scale at Week 12 and Week 16 will be compared between each of the bermekimab groups and the placebo group.
- The proportion of participants who achieved PGI-s of normal (0), normal (0) or mild (1) at Week 12 and Week 16 will be compared between each of the bermekimab groups and the placebo group respectively.
- Summary of PGI-s symptom status will be summarized over time.

## 5.4.3.6. Exploratory Endpoints

In addition to the above efficacy analyses, the follow efficacy analyses and summaries will be explored :

## 5.4.3.6.1. International Hidradenitis Suppurativa Severity Score System (IHS4)

## 5.4.3.6.1.1. Definition

IHS4 is a dynamic severity assessment of HS. IHS4 score is arrived at by the number of nodules (multiplied by 1) plus the number of abscesses (multiplied by 2) plus the number of draining tunnels (multiplied by 4). A total score of 3 or less signifies mild, 4-10 signifies moderate and 11 or higher signifies severe disease.

#### 5.4.3.6.1.2. Analysis Related to IHS4

- The change from baseline in international hidradenitis suppurativa severity score at Week 12 and Week 16 will be compared between each of the bermekimab groups and the placebo group.
- The change from baseline in international hidradenitis suppurativa severity score will be summarized over time by treatment group.

#### 5.4.3.6.2. Hidradenitis Suppurativa Quality of Life Measure (HiSQOL)

#### 5.4.3.6.2.1. Definition

HiSQOL is a patient self-reported questionnaire that assesses various HS-related quality of life measures. This instrument includes 17 items that are categorized into 3 subscales as 'Symptom', 'Psychosocial', and 'Activities'. A five-point item response scale incorporating 'extremely', 'very much', 'moderately', 'slightly' or 'not at all' was used for all items. The point values assigned to these responses were 4, 3, 2, 1 and 0, respectively. For some items, respondents were given the additional option of 'unable to do, due to my HS' and/or 'I do not normally do this, HS did not influence'. The former option was assigned a score of 4 to indicate the severity of the impact of HS, whereas the latter option was assigned a score of 0 to indicate that HS did not impact it.

## 5.4.3.6.2.2. Analysis Related to HiSQOL

- The change from baseline in HiSQOL and HiSQOL subscales at Week 12 and Week 16 will be compared between each of the bermekimab groups and the placebo group.
- The change from baseline in HiSQOL and HiSQOL subscales will be summarized over time by treatment group.

# 5.4.3.6.3. Physician's Global Assessment of Inflammatory Skin Disease (PGA-ISD)

## 5.4.3.6.3.1. Definition

The PGA-ISD is a tool developed by the International Dermatology Outcome Measures (IDEOM) organization to serve as a potential standardized outcome measure for assessment of inflammatory skin diseases.

- PGA-ISD score of 0: No inflammatory activity
- PGA-ISD score of 1: Barely discemible inflammatory activity
- PGA-ISD score of 2: Mild inflammatory activity
- PGA-ISD score of 3: Moderate inflammatory activity
- PGA-ISD score of 4: Severe inflammatory activity
- PGA-ISD score of 5: Extremely severe inflammatory activity

## 5.4.3.6.3.2. Analysis Related to PGA-ISD

- The distribution of the PGA-ISD score at Week 12 and Week 16 will be compared between each of the bermekimab groups and the placebo group and will be summarized over time.
- The proportion of participants who achieved PGA-ISD score of no inflammatory activity (0), no inflammatory activity (0) or barely discemible inflammatory activity (1) or PGA-ISD score of mild inflammatory activity or better (≤ 2) at Week 12 and Week 16 will be compared between each of the bermekimab groups and the placebo group respectively.
- The proportion of participants who achieved PGA-ISD score of no inflammatory activity (0), no inflammatory activity (0) or barely discemible inflammatory activity (1) or PGA-ISD score of mild inflammatory activity or better (≤ 2) will be summarized over time by treatment group.

## 6. SAFETY

Safety will be assessed by summarizing the incidence and type of AEs and examining changes in laboratory parameters (hematology, chemistry, and inflammatory markers), and vital signs.

In all the safety analysis, randomized participants who received at least 1 (partial or complete) dose of study agent administration will be included. For safety analyses, participants will be analyzed according to the randomized treatment groups they were assigned to, regardless of the treatments they actually received. No formal statistical comparison is planned.

Depending on the safety data categories, the cumulative safety data will be analyzed through different study periods through Week 16 and Week 36. Unless otherwise specified, tabular summaries of safety events for key study periods are in general presented as following:

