10.3 ANALYSIS SETS

- The safety analysis set (SAF) population will consist of all patients who receive at least one dose of study medication and will be analyzed as treated.
- The modified intent-to-treat (mITT) population will consist of all randomized and treated patients.

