10.5.2 Safety Analysis

The primary objective of this study is to evaluate the safety and efficacy of bermekimab. Safety endpoints will be evaluated by monitoring adverse events from clinical and laboratory reporting. The safety analysis will be based on the SAF population. A summary of safety results will be presented for each treatment group.

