10.5.3 Efficacy Analysis

In general, efficacy analyses will include all randomized and treated patients (mITT population) and will be analyzed based on the randomized treatment groups, regardless of the treatment they actually received.

In addition to the analyses that will be performed following the formal database lock at the end of the study at Week 36, an additional database lock may be performed at Week 16, and interim analyses utilizing unblinded efficacy data available as the study progresses, may also be conducted to help plan potential future development activities. An internal interim analysis committee (IAC) will be established to review the interim data and formulate recommended decisions/actions. The IAC will consist of at least a clinician and a statistician (neither of whom are involved in study conduct or compound development), one of whom will chair the committee, and may also include other members as required by the nature of the IAs. Details will be provided in a separate IAC charter, which will define the organization and roles and responsibilities of the committee, possible recommendations or requests, and the communication process following IA reviews. Results from the Week 16 DBL and/or interim analyses will not be disseminated to investigators or subjects participating in the study. In addition, results of the interim analyses will not be disseminated to individuals associated with the conduct of the study.

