## Summaries through Week 16 (placebo controlled):

Safety data through Week 16 will be summarized by treatment groups

- 1. Placebo
- 2. Bermekimab 400 mg q2w
- 3. Bermekimab 400 mg qw
- 4. Combined Bermekimab

This allows between-group comparisons of safety between the bermekimab regimens and the placebo group based on similar follow-up period in each group.

#### Summaries through Week 36

Safety data through Week 36 will be summarized by treatment groups including

- 1. Placebo  $\rightarrow$  bermekimab 400 mg qw
- 2. Bermekimab 400 mg q2w
- 3. Bermekimab 400 mg qw
- 4. Combined Bermekimab

This allows safety comparisons between each bermekimab regimen through Week 36 based on the similar follow-up time in each group.

The list of actual treatment groups for safety analyses and inclusions of participants and safety events/measurements in each group are defined as follows:

- 1. **Placebo:** all participants who were randomized to placebo at Week 0 and received treatment with placebo only or received treatment with placebo prior to receiving treatment with bermekimab. For participants who started treatment with placebo but later received bermekimab, the safety events/measurements on and after the first dose of bermekimab will be excluded from this group. Only the safety events/measurements that occurred while the participants had been receiving placebo only will be included in this group.
- Placebo → bermekimab 400 mg qw: All participants who were randomized to placebo at Week 0 started treatment with placebo only and later crossed over to receive treatment with bermekimab 400 mg SC (qw). Only the safety events/measurements from these participants that occurred on and after their first administration of bermekimab will be included in this group.
- 3. **Bermekimab 400 mg q2w:** all participants who were randomized to bermekimab 400 mg SC (q2w) at Week 0 and received bermekimab. All the safety events/measurements from these participants that occurred from Week 0 will be included in this group.
- 4. **Bermekimab 400 mg qw:** all participants who were randomized to bermekimab 400 mg SC (qw) at Week 0 and received bermekimab. All the safety events/measurements from these participants that occurred from Week 0 will be included in this group.

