## 7. PHARMACOKINETICS/PHARMACODYNAMICS

## 7.1. Pharmacokinetics

All PK analyses will be based on the PK analysis set (Section 2.4.3). Participants will be analyzed according to the randomized treatment groups they were assigned to, regardless of the treatments they actually received. Unless otherwise specified, tabular summaries of PK for key study periods are in general presented as following:

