## 7.1.1.1. Data Handling Rules

Unless otherwise specified, the following data handling rules will apply to PK analyses:

- Participants will be analyzed according to the treatment groups that they actually received.
- All concentration summaries for a particular timepoint will include data obtained from treated participants at the timepoint of interest without imputing any missing data.
- A concentration not quantifiable (below the lower limit of quantification) will be treated as 0 in the summary statistics and shown as the lower limit of quantification (< LLOQ) in the data listings.
- The data from a participant who meets 1 of the following dosing deviation criteria (if applicable) will be excluded from the by-visit data analyses from that point onwards:
- Discontinue bermekimab administrations.
- Skipped a bermekimab administration.
- Received an incomplete/ incorrect dose (if applicable).
- Received an incorrect study agent (if applicable).
- Received an additional bermekimab dose.

In addition, if a participant has an administration outside of dosing windows (Table 2), the concentration data collected at and after that visit will be excluded from the by-visit data analyses. Additional exclusions for incongruous PK data to be implemented based on Janssen SOP-07948. All participants and samples excluded from the analysis will be clearly documented in the Clinical Study Report.

Visit	Window
Week 0 through Week 32	$\pm$ 3 days from scheduled visit day
Final Safety and Efficacy Follow-up visit	$\pm$ 7 days from scheduled visit day

Table 2:	Dosing Window
----------	---------------

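### SAP Section 6 groups safety data by randomized arm, contradicting the protocol's as-treated rule and the SAP's own group definitions, so a misdosed participant's events could be misplaced or lost

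*SAP*

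**What the plan says.** Protocol 10.3 defines the safety population as "all patients who receive at least one dose of study medication and will be analyzed as treated". Protocol 10.5.2 adds: "The safety analysis will be based on the SAF population". The as-randomized rule appears in the protocol for efficacy: under 10.5.3, the mITT patients "will be analyzed based on the randomized treatment groups, regardless of the treatment they actually received".

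SAP Section 6 carries that rule over to safety: "For safety analyses, participants will be analyzed according to the randomized treatment groups they were assigned to, regardless of the treatments they actually received". The same paragraph says that every randomized participant with at least one partial or complete dose is included. SAP 2.4.2 defines who is in the safety set but not how its members are grouped.

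Later in Section 6 the SAP lists what it calls actual treatment groups. The Placebo group takes in "all participants who were randomized to placebo at Week 0 and received treatment with placebo only", or placebo before bermekimab, and drops their events from the first bermekimab dose onward. The crossover group must have been randomized to placebo, started on placebo only and then crossed over. Each bermekimab group must have been randomized to that regimen and have received bermekimab. A Combined Bermekimab column is listed for the tables but not defined among these groups.

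PK has a similar conflict. SAP 7.1 says "Participants will be analyzed according to the randomized treatment groups they were assigned to, regardless of the treatments they actually received", while SAP 7.1.1.1 says "Participants will be analyzed according to the treatment groups that they actually received".

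**The concern.** The protocol and SAP give opposite grouping rules for safety. Protocol Section 10 is meant to be the basis for the SAP. Where the SAP departs from it on multiplicity (SAP 5.2.1), it says so and explains why; here it says nothing, which looks like an oversight.

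SAP Section 6 is also inconsistent within itself. Its opening text disregards treatment received and includes every dosed participant, but its group definitions all depend on receipt. Two programmers could build different tables from the same section.

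Safety is part of the primary objective (protocol 10.5.2, SAP 1.1), and Section 6 says its tables are meant to allow comparison of the bermekimab regimens with placebo. Misdosing is foreseen: SAP 4.5 lists wrong treatment or incorrect dose as a major deviation, Arm 2 alternates active and placebo injections, and the COVID-19 appendix permits self-administration at home. Adverse events are among the data in the Week 16 lock (SAP 2.4), when selected sponsor staff are unblinded (SAP 1.5.2). A grouping rule chosen after that point would be open to criticism.

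**Working it through.** The plan states no figure on this point, so the check is mainly one of logic. I applied each of the two rules in SAP Section 6 literally to each pattern of assignment and receipt.

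| Randomized to | Received | If the opening sentence governs | If the group definitions govern |
|---|---|---|---|
| Placebo | Placebo only, or crossover as planned | Placebo, then crossover column | The same |
| Placebo | Bermekimab in error at the first dose | Placebo | No column: no placebo came before bermekimab, and treatment did not start with placebo only |
| Placebo | Stray bermekimab dose before Week 16, after starting placebo | Placebo throughout | Placebo up to that dose; later events are excluded and the through-Week-16 table has no column for them |
| qw or q2w | Placebo only | Randomized bermekimab arm | No column: bermekimab was never received, and the arm was not placebo |
| qw or q2w | Placebo first in error, bermekimab later | Randomized arm | Randomized arm, including events before any bermekimab |
| q2w | Dosed as qw | q2w | q2w |

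Three results follow.

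1. Without misdosing (first row) the two rules agree, and both match an as-treated analysis.
2. The definitions are not exhaustive. The second and fourth rows describe people who are in the safety set under SAP 2.4.2 but in none of the defined groups. This conflicts with the statement in SAP 6.1 that every reported treatment-emergent event is analysed.
3. In the third row, events after the stray dose are missing from the placebo-controlled summary even if the participant later crosses over as planned. Without that crossover they are in no defined group.

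Size per participant. SAP 1.4 plans about 150 participants at 1:1:1, so about 150/3 = 50 per arm. Let p be an arm's event rate.

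- Removing a participant who had the event changes the rate by p − (50p − 1)/49 = (1 − p)/49.
- Removing a participant without the event changes it by 50p/49 − p = p/49.
- At p = 10% these are 0.90/49 = 1.8 points and 0.10/49 = 0.2 points. At p = 50% both are 0.50/49 = 1.0 point.
- The largest value is reached when the participant removed had the arm's only event: p = 1/50, giving 0.98/49 = 2.0 points.
- If the event is lost but the participant stays in the denominator, the change is 1/50 = 2.0 points.

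One participant therefore changes an arm's event rate by at most about 2 percentage points, and often by less.

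**The case against.** The best defence is that specific text overrides general text. The Placebo definition removes everything from the first bermekimab dose onward, so bermekimab events would not reach the placebo column. That is a fair reading, but it is the one that leaves some participants and events in no column. A reader might infer that the SAP both counts bermekimab events under placebo and drops them. It does not: the two harms come from competing readings of Section 6, and only one can apply.

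The no-column cases are also narrow. One needs bermekimab at a placebo participant's first dose. The other needs a bermekimab participant who received no active dose despite two active loading visits. Home administration under the COVID-19 appendix is only an option. No formal safety comparison is planned. SAP 6.1 lists participants with SAEs, events of grade 3 or higher, discontinuations due to AEs, anaphylactic or serum sickness-like reactions, and deaths. SAP 4.5 summarizes and lists major deviations, including wrong treatment. All of this stands. It limits the consequence but does not remove the conflict.

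A reader might call as-randomized grouping the non-conservative choice for safety. The documents do not show that; the direction depends on who was misdosed and who had an event.

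A reader might also infer that the PK results are compromised. SAP 7.1.1.1 removes from by-visit analyses, from that point on, anyone given an incorrect agent, an incorrect dose or an additional dose, so the grouping rule rarely changes a by-visit PK summary. SAP 7.2 groups immunogenicity as randomized, and nothing in that section contradicts it.

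Finally, the protocol's as-treated rule does not say how to place mixed exposure, so keeping a q2w participant who received extra active doses in q2w is not shown to breach it.

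**Conclusion.** The point holds as a wording conflict that should be settled before unblinding. SAP Section 6 contradicts protocol 10.3 without explanation, and it contradicts its own group definitions. Depending on which SAP text governs, a misdosed participant's events would be counted in the wrong column or in none.

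The effect is zero if nobody is misdosed. The documents give no misdosing rate, so the total effect is unknown and probably small. The bound of about 2 percentage points per participant assumes about 50 per arm; it is a ceiling, not the shift to expect each time. It matters most for uncommon events, where one case is a large share of an arm's count. The documents do not support saying that the safety conclusions would be wrong.

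**What to change.** Before the Week 16 unblinding:

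- Replace the as-randomized sentence in SAP Section 6 with the protocol's as-treated rule, and add that rule to SAP 2.4.2.
- Redefine the safety groups by agent and regimen actually received, so that every dosed participant and every event falls in a defined column of each table. Define the Combined Bermekimab column at the same time.
- State how mixed exposure is assigned. One option is the regimen predominantly received, with events after a first bermekimab dose never counted as placebo; the rule must then name the column that takes those events.
- Reconcile SAP 7.1 with 7.1.1.1 for PK. Changing SAP 7.2 for immunogenicity is optional, for consistency.

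The cost is SAP wording plus minor derivation and programming work, mainly for the mixed-exposure rule. Trial conduct and data collection do not change.
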